#### **9.4.3.3. PK Analyses of Sasanlimab**

Concentrations for sasanlimab will be summarized descriptively (n, mean, SD, coefficient of variation (CV), median, minimum, maximum, geometric mean, its associated CV, and 95% confidence interval) by arm, cycle, and day.

PK parameters including  $C_{\text{trough}}$ ,  $C_{\text{max}}$ ,  $T_{\text{max}}$ , and AUC for sasanlimab will be determined from the respective concentration-time data using standard non-compartmental methods as data permit. Additionally, if data permit or if considered appropriate, PK parameters such as  $t_{1/2}$ , CL, and  $V_d$  will also be estimated. Actual sample collection times will be used for the parameter calculations. Non-compartmental PK parameters, when calculated, will be summarized descriptively by sub-study and cycle.

The trough concentrations for sasanlimab will be plotted for each combination arm using a box whisker plot by cycle and day to assess the attainment of steady state.

Summary data may be compared with the historical data of sasanlimab and combination study drugs as single agents to assess any potential drug interaction effects.

#### **9.4.3.4. Analysis of Immunogenicity Data of Sasanlimab**

For the immunogenicity data, the percentage of participants with positive ADA and NAb (if analyzed) each will be summarized by dose level or by treatment. For participants with positive ADA or NAb, the magnitude (titer), time of onset, and duration of ADA or NAb response will also be described, if data permit.

### **9.4.4. Exploratory Endpoints**

#### **9.4.4.1. Analyses of Biomarker Endpoints**

Summary statistics (eg, the mean and standard deviation, median, and minimum/maximum levels of continuous, and frequencies and percentages of categorical biomarker measures) will be determined for baseline and on-treatment biomarkers. Those biomarkers showing significant association (at significance level of 0.05) with objective response rate will be used to define participant subgroups for time-to-event analyses. Further details will be specified in the SAP.

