settings where safety and efficacy are known to be contingent on a particular biomarker test result. In settings where the relationships between safety, efficacy, and biomarker test results are either unknown or may be different from the relationships observed for the single-agent components, enrollment may not be based on a test result but retrospective analysis will be used to assess the level of heterogeneity in biomarker-defined subgroups. If such retrospective analysis suggests that the target benefit is only seen in a defined subpopulation, then enrollment into future cohorts could be based on prospective confirmation that participants are members of that subpopulation. These new cohorts will be included in the study via protocol amendment. Control arms may be included within sub-studies to this master study and may be applied to specific treatment settings, where an understanding of the contribution of the individual components of a higher order combination is needed.

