### **8.7. Genetics**

#### **8.7.1. Specified Genetics**

Genetic assessments for all sub-studies will be performed utilizing tumor and blood samples as collected and described in the respective sub-study SoAs.

*Biospecimen to confirm eligibility:* DNA samples may be analyzed for the purpose of confirming the presence of DNA alterations (eg, BRAFV600E) if required for enrollment to the study arm.

In the event of DNA extraction failure, a replacement genetic blood sample may be requested from the participant, or the participant's tumor biopsy may be used to confirm the presence

of the DNA alterations. See the Genetics section of the individual sub-studies for additional details of the eligibility assessments.

*Baseline tumor biopsy:* Whole exome sequencing of participant's tumor biopsy will be performed on qualifying specimens to characterize DNA alterations that may be associated with response to therapy. TCR sequence analysis may be performed on qualifying tumor biopsies to assess associations between tumor-associated TCRs and clinical outcomes.

*Blood for cell-free DNA analysis:* samples may be analyzed for epigenetic and/or genetic associations with clinical outcomes.

*Blood for specified genetic research:*

Whole genome sequencing of participants' blood samples collected prior to initiation of study therapy may be performed to confirm somatic vs germline nature of DNA alterations detected in matched tumor samples. Whole genome sequencing of samples may also be performed to characterize epigenetic modifications of DNA. Genetic variation at specific loci (such as FCGR genes) or epigenetic modifications in peripheral blood may also be assessed by targeted assays using PCR or NGS-based methods applied to white blood cells or cell-free DNA.

*Blood for TCR analysis:* A separate peripheral blood specimen will be collected to monitor the T Cell Receptor repertoire over the first 2 cycles of therapy according to the [SoA](#) of each sub-study.

The sequencing methods will not have been validated for diagnostic use to assess predisposition to genetic disease. Details on processes for collection and shipment of these samples can be found in the laboratory manual.

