### **8.8.1. Specified Gene Expression (RNA) Research**

RNA may be isolated from qualifying tumor and blood specimens. The isolated RNA may be subjected to next-generation sequencing in order to define transcriptome profiles associated with effect of study treatment or clinical outcomes.

Details on processes for collection and shipment of these samples can be found in the laboratory manual.

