### 9.3. Analysis Set

For purposes of analysis, the following analysis sets are defined:

Participant Analysis Set	Description
Full analysis set	The full analysis set includes all participants who receive at least 1 dose of study drug. Participants will be classified according to the treatment actually received.
Safety analysis set	The safety analysis set includes all participants who receive at least 1 dose of study drug. Participants will be classified according to the study treatment actually received. In a non-randomized study the full analysis set and safety analysis set are identical.
Per-protocol analysis set	The per-protocol analysis set is a subset of the full analysis set and will not include participants who do not meet criteria that could impact the key objectives of the study. These criteria will be pre-specified in the statistical analysis plan. The per protocol analysis set will be used for sensitivity analyses of the primary efficacy endpoint.
DLT-Evaluable analysis set	The DLT-evaluable analysis set includes all participants who receive at least 1 dose of study treatment in the Phase 1b and either experience DLT during the DLT-observation period or complete the DLT-observation period without DLT. Participants without DLTs receive less than 75% of the planned dose of each study drug in during the DLT observation period for reasons other than treatment-related toxicity are not evaluable for DLT. All participants deemed non-evaluable for DLT may be replaced.
Biomarker analysis set	The biomarker analysis set for each biomarker is a subset of the safety analysis set and includes all participants with at least 1 biomarker evaluated pre-dose.
Pharmacodynamic analysis set	The pharmacodynamic analysis set is a subset of the safety analysis set and includes participants with at least 1 biomarker evaluated pre- and post-dose.
Immunogenicity analysis set	The immunogenicity analysis set is a subset of the safety analysis set and includes participants who have at least 1 analyzed sasanlimab ADA/NAb sample.
PK analysis set	The PK concentration analysis set is a subset of the safety analysis set and will include participants who have at least 1 concentration measurement for the measured analytes related to the study drug (ie, sasanlimab, etc).

Participant Analysis Set	Description

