**Table 6. Sub-Study A Objectives and Endpoints**

Objectives	Endpoints

 
To evaluate the immunogenicity of sasanlimab when given in combination with encorafenib and binimetinib.
 
	
 
ADA and NAb (ie, incidence) against sasanlimab, as data permit.
 

 
To assess the association between anti-tumor activity and PD-L1 expression in baseline tumor biopsies.
 
	
 
OR by PD-L1 expression in baseline tumor samples.
 

 
To assess the effects of sasanlimab, encorafenib, and binimetinib on patient-reported health-related quality of life.
 
	
 
Health-related quality of life as measured by EORTC QLQ-C30/LC13
 

Exploratory:	Exploratory:
Phase 1b and Phase 2	Phase 1b and Phase 2

 
To understand the relationship between the therapeutic intervention(s) being studied and the biology of the participant's disease.
 
	
 
Biomarkers, consisting of DNA, RNA, protein, metabolites or defined cell types, resulting from analyses of peripheral blood and/or tumor tissue biospecimen obtained at baseline, on treatment or at end-of-study.
 

Phase 2	Phase 2

 
To assess additional measure of anti-tumor activity of sasanlimab in combination with encorafenib and binimetinib.
 
	
 
Depth of response by investigator assessment using RECIST v1.1.
 

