#### **12.9.1.3.2. Phase 2 Dose Expansion**

Approximately 62 participants will be enrolled in the Phase 2 part of Sub-Study A.

Phase 2 will test the null hypothesis that the durable ORR does not exceed 35% ( $H_0$ : durable ORR  $\leq 35\%$ ). The null hypothesis will be tested against the alternative ( $H_1$ : durable ORR  $> 35\%$ ) at one-sided level of significance  $\alpha = 0.025$  using the binomial distribution.

Sixty-two (62) participants will provide at least 90% power to reject the null hypothesis if the true durable ORR is at least 55% (durable ORR  $\geq 55\%$ ).

At the end of Phase 2:

- If there are  $\leq 29$  objective durable responders of 62 participants in the Phase 2 part, then it will be declared that the null hypothesis cannot be rejected.
- If there are  $\geq 30$  objective durable responders of 62 participants in the Phase 2 part, then the null hypothesis will be rejected.

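### Section 9.4.4.1 picks biomarkers by a 0.05 test against response, then reads PFS subgroups in the same participants, so a noise marker that passes shows a biased PFS difference

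*Protocol*

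**What the plan says.** Under the exploratory endpoints of the master protocol, section 9.4.4.1 covers baseline and on-treatment biomarkers. It states: "Those biomarkers showing significant association (at significance level of 0.05) with objective response rate will be used to define participant subgroups for time-to-event analyses". The next sentence defers: "Further details will be specified in the SAP". The section gives no marker list, multiplicity adjustment, hold-out sample or second data set. Sections 12.9.1.5.2.5 and 13.9.1.5.2.5 adopt it by reference for both sub-studies.

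Section 9.3 defines one analysis set per marker: "The biomarker analysis set for each biomarker is a subset of the safety analysis set". Selection and the time-to-event comparison therefore use the same people.

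The marker classes are open-ended. Table 6 lists "Biomarkers, consisting of DNA, RNA, protein, metabolites or defined cell types, resulting from analyses of peripheral blood and/or tumor tissue biospecimen". Section 8.7.1 says that tumor whole exome sequencing "will be performed on qualifying specimens to characterize DNA alterations that may be associated with response to therapy". Section 8.8.1 adds, permissively: "The isolated RNA may be subjected to next-generation sequencing in order to define transcriptome profiles".

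On use of the results, section 2.1 has a clause beginning "If such retrospective analysis suggests that the target benefit is only seen in a defined subpopulation". It goes on to allow enrollment into future cohorts to be limited to that subpopulation, through a protocol amendment.

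**The concern.** Two features of the rule combine badly.

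First, a flat 0.05 per marker across an unstated and possibly long list lets some noise markers through.

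Second, a noise marker passes because responders happened to fall on one side of it. Responders tend to progress later. A confirmed response also requires a second qualifying assessment at least 4 weeks later (section 10.9), while PFS ends at progression or death. The imbalance that got the marker selected therefore reappears as a PFS difference in the same direction. A reader who sees a response association followed by a PFS separation may take the second as support for the first, when it is largely the same information.

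The gate may also point the wrong way. Section 2.2 expects the targeted agents to act on ORR and sasanlimab to act on DR, PFS and OS. A marker of durable benefit with no relation to response is never carried to the time-to-event analyses.

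**Working it through.** Section 9.4.4.1 contains no derived figure to reproduce; 0.05 is a design input.

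**Inputs from the protocol.** Screening level 0.05 (9.4.4.1). N = 62: "Approximately 62 participants will be enrolled in the Phase 2 part of Sub-Study A" (12.9.1.3.2). Response rate 64%, the rate that 12.2.1 reports for the standard doublet.

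**Assumptions.** Number of markers m (not stated, shown as a range). Null binary marker with 50% prevalence. Exponential PFS with median about 10 months. Censoring either random or at 24 months. Responder versus non-responder PFS hazard ratio from 1.0 (no link) to 0.2.

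**Step 1: entry to subgroup analysis.** For m independent null markers, the expected number of false selections is 0.05m and P(at least one) = 1 − 0.95^m.
- m = 10: 0.5 expected, P = 0.40
- m = 20: 1.0 expected, P = 0.64
- m = 100: 5 expected, P = 0.99

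**Step 2: bias in PFS once a null marker has passed.** Simulated null markers were tested against response at 0.05. PFS was then compared by marker in the same participants. The true hazard ratio is 1.0, and ranges span the two censoring patterns.

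| Responder PFS HR (assumed) | Log-rank rejection among selected markers | Median spurious HR |
|---|---|---|
| 1.0 | about 5.5–6% | about 1.0 |
| 0.5 | about 8–10% | about 1.2 |
| 0.3 | about 14–16% | about 1.4 |
| 0.2 | about 18–21% | about 1.5 |

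Without selection the log-rank test rejects about 5%, so the excess comes from the selection. At responder HR 0.3 and random censoring, 83% of the selected noise markers show PFS in the same direction as response.

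**Step 3: both steps together.** A given null marker passes the gate and then reaches log-rank significance with probability of about 0.05 times the rate in the table:
- responder HR 0.5: 0.05 × 0.08 = 0.4%
- responder HR 0.3: 0.05 × 0.14 = 0.7%
- responder HR 0.2: 0.05 × 0.21 = about 1%

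With 20 independent null markers at 0.7% each, P(at least one passes both) = 1 − 0.993^20 = about 0.13.

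**Step 4: would a correction at the gate be enough?** With m = 20, a Bonferroni threshold of 0.05/20 = 0.0025 gives 1 − 0.9975^20 = 0.049 for at least one false entry. That controls the count. It does not remove the same-data bias in any marker that still passes, because such a marker is by construction unbalanced between responders and non-responders.

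**The case against.** The case on the other side is substantial, and most of it stands.

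- **The step is exploratory.** It touches no primary test, dose decision or futility rule. The SAP is not shown and could add a marker list and a correction; the protocol's silence does not prove that none is planned. But the sequence itself, response gate then survival subgroups in the same set, is protocol text, and Step 4 shows that a correction at the gate leaves the bias in place.
- **No test between subgroups is specified.** The plan is Kaplan-Meier with point estimates and 95% CIs. The rejection rates above are therefore conditional on someone applying a log-rank test. The Kaplan-Meier curves carry the same bias without a p-value.
- **The gate reduces the number of survival comparisons.** A null marker passes both steps about 1% of the time or less, against about 5% for an ungated PFS test. A reader might infer from the 0.64 or 0.99 that false PFS findings are nearly certain. Those figures count entry to an exploratory display and nothing more.
- **OS and DR.** A reader might extend the bias to all time-to-event endpoints. Section 2.2 calls ORR an unreliable predictor of OS, so the effect there may be small, and OS was not simulated. DR is measured among responders only and is not shown to be affected.
- **Enrollment.** A reader might infer that a false marker could directly restrict a cohort. Section 2.1 says only that enrollment could be so based, requires a protocol amendment, and does not refer to the 9.4.4.1 rule.
- **Marker breadth.** RNA work is optional. The blood draws for RNA, protein and metabolomic research were withdrawn from both sub-studies, and baseline tumor tissue is collected in Phase 2 only. Exome sequencing, T-cell receptor and cell-free DNA work remain.

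**Conclusion.** The point holds in limited form. As written, the rule selects markers on response with no stated multiplicity control and then describes PFS in the same participants, which biases PFS differences for any noise marker that passes. The size is a median spurious hazard ratio of about 1.2 to 1.5 for an assumed responder hazard ratio of 0.5 to 0.2, at N = 62 and 64% response. It disappears if response and PFS are unrelated. These figures rest on assumed marker prevalence, PFS distribution, censoring and strength of the response–PFS link; the number of markers is unknown.

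The documents do not support reading this as a threat to the trial's main conclusions, as a demonstrated OS problem, or as an automatic route to restricted enrollment. It is a poorly chosen exploratory method that is cheap to improve, and the response gate also fits badly with the protocol's own expectation of where sasanlimab will show its effect.

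**What to change.** In section 9.4.4.1, replace the response gate. For each baseline marker, estimate the association with PFS and OS directly in all biomarker-evaluable participants, as a hazard ratio with a confidence interval, and apply Benjamini-Hochberg false-discovery control across all markers tested. If any subgroup is still chosen by its association with response, state that its PFS result is not independent evidence, and that this applies equally to any cohort decision under section 2.1.

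A mandatory second data set before such a decision would go further than an exploratory step needs, given that an amendment is already required.

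The cost is one paragraph in 9.4.4.1, carried into the SAP, with no new data, visits or participants. The downside is that fewer markers will be declared significant.

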The scientific rationale for each of the agents combined with sasanlimab in this study is based on the potential to stimulate anti-tumor immunity and/or increase tumor susceptibility to immune attack. Each sub-study will be comprised of a Phase 1b component to evaluate initial safety and a Phase 2 component to evaluate anti-tumor activity and additional safety. It is initially anticipated that 5 combinations will be explored in this umbrella protocol to provide scientific focus (Figure 1). It is also anticipated that data from this study may be used to inform the design of additional clinical trials.

Participant subgroups will be prioritized for treatment with a given combination based on available data regarding the ability of the combination to prevent, bypass, or reverse resistance to PD-1/PD-L1 therapy. Prospective biomarker testing will be employed in settings where safety and efficacy are known to be contingent on a particular biomarker test result. In settings where the relationships between safety, efficacy, and biomarker test results are either unknown or may be different from the relationships observed for the single-agent components, enrollment may not be based on a test result but retrospective analysis will be used to assess the level of heterogeneity in biomarker-defined subgroups. If such retrospective analysis suggests that the target benefit is only seen in a defined subpopulation, then enrollment into future cohorts could be based on prospective confirmation that participants are members of that subpopulation. These new cohorts will be included in the study via protocol amendment. Control arms may be included within sub-studies to this master study and may be applied to specific treatment settings, where an understanding of the contribution of the individual components of a higher order combination is needed.

Please refer to the sub-study appendices for the rationale of each sub-study.

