#### **13.8.4. Biomarkers**

PD-L1 protein expression in NSCLC is determined by using TPS, which is the percentage of viable tumor cells showing partial or complete membrane staining at any intensity. The specimen should be considered to have PD-L1 expression if TPS  $\geq 1\%$  and high PD-L1 expression if TPS  $\geq 50\%$ .

Results of the local laboratory PD-L1 results will be entered in the CRF.

In Phase 2, blood samples or tumor tissue will also be tested centrally to confirm PD-L1 status and for exploratory biomarker analyses. Tumor tissue testing is described in [Section 8.8](#). Tumor tissue collected after the participant was diagnosed with metastatic disease is preferred. The tumor tissue sample must not be from locations that were previously irradiated.

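### Section 9.4.4.1 commits response-associated continuous biomarkers to subgroups for the time-to-event analyses and to no analysis on the measured scale; a median split would lose about 36% of the information.

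*Protocol*

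**What the plan says.** Protocol Section 9.4.4.1, under exploratory endpoints, plans descriptive summaries of baseline and on-treatment biomarkers. It names both scales: "levels of continuous, and frequencies and percentages of categorical biomarker measures". It then sets a two-step rule. "Those biomarkers showing significant association (at significance level of 0.05) with objective response rate" are selected, and these "will be used to define participant subgroups for time-to-event analyses". The section closes with "Further details will be specified in the SAP".

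Other parts of the protocol bear on this:

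- **Markers.** Table 6 lists "Biomarkers, consisting of DNA, RNA, protein, metabolites or defined cell types" for Sub-Study A, and Table 24 does the same for Sub-Study B. Some of these are categorical by nature and others are measured on a continuous scale.
- **Stated cut-points.** Section 13.8.4 gives cuts for PD-L1 only: "The specimen should be considered to have PD-L1 expression if TPS" is at least 1%, and high expression starts at 50%.
- **Endpoints and method.** Sections 12.9.1.5.2.1 and 13.9.1.5.2.1 analyse DR, PFS and OS by Kaplan-Meier.
- **Possible use.** The master protocol rationale (Sections 1.1 and 2.1) says that, where enrolment is not based on a test result, "retrospective analysis will be used to assess the level of heterogeneity in biomarker-defined subgroups". Later cohorts could be restricted on the strength of that analysis, by protocol amendment.
- **Sample sizes.** Phase 2 has about 62 participants in Sub-Study A (Section 12.9.1.3.2) and 20 in each of three arms in Sub-Study B (Section 13.9.1.3.2).

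**The concern.** The cut-points are left open, but the decision to group is not. A continuous marker that passes the response screen is to enter the time-to-event analyses as a set of categories. Everyone on one side of a cut is then treated alike, and the gradient within each group is thrown away. Outside PD-L1 the protocol gives no reason for grouping.

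The samples are small, and the results may feed into who is enrolled later. A real relation between a marker and PFS, DR or OS is more likely to be missed, or estimated imprecisely, than it would be if the measured value were used.

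**Working it through.** **The plan's own figure.** There is none to reproduce. The protocol states no biomarker effect, event count, cut-point or power for these analyses.

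**Inputs.** From the protocol: 62 participants (Sub-Study A) and 20 per arm (Sub-Study B). Assumed: a normally distributed marker, a log-hazard linear in the marker, a two-sided 5% test, a hazard ratio per SD of 1.3 to 2.0, and 20 to 62 events.

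**Step 1: information kept by one cut.** For a cut at quantile q of a normal marker, efficiency relative to the measured value is φ(z_q)² / [q(1 − q)]. At the median this is 0.3989² / 0.25 = 2/π = 0.637, a loss of 36.3%.

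**Step 2: power after the cut.** Power = Φ(ncp × √efficiency − 1.960). If the measured value would give 80% power, ncp = 1.960 + 0.842 = 2.802. With a median split, 2.802 × √0.637 − 1.960 = 0.276, and Φ(0.276) = 60.8%.

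| Grouping | Efficiency | Information lost | 80% power becomes |
|---|---|---|---|
| Median split | 0.637 | 36% | 60.8% |
| 25/75 | 0.539 | 46% | 53.8% |
| 20/80 | 0.490 | 51% | 50.0% |
| 10/90 | 0.342 | 66% | 37.4% |
| Three equal ordered groups, scored | 0.793 | 21% | about 70% |
| Four equal ordered groups, scored | 0.861 | 14% | about 74% |

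The last two powers use the same formula: 2.802 × √0.793 − 1.960 = 0.535, and 2.802 × √0.861 − 1.960 = 0.640. A marker that is categorical by nature is not cut and loses nothing.

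**Step 3: dependence on starting power.** With a median split, 90% falls to 73.4%, 50% to 34.6% and 30% to 20.8%. These are losses of 17, 15 and 9 points.

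**Step 4: illustrative event counts.** With ncp = √events × ln(HR per SD), 50 events and HR 1.5 give 7.071 × 0.405 = 2.87. Power is 81.8% on the measured value and 62.8% with a median split. Over 20 to 62 events and HR 1.3 to 2.0, the loss by formula runs from about 1 to 19 points.

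**Step 5: simulation check.** Cox score tests, 8,000 trials per row, uniform censoring:

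| n | HR per SD | Mean events | Measured value | Median split | Loss (points) |
|---|---|---|---|---|---|
| 62 | 1.5 | about 49 | 76.2% | 55.8% | 20 |
| 62 | 1.6 | about 49 | 87.4% | 68.4% | 19 |
| 62 | 2.0 | about 48 | 99.0% | 92.5% | 7 |
| 20 | 1.5 | about 16 | 30.4% | 21.1% | 9 |
| 20 | 2.0 | about 15 | 65.1% | 44.5% | 21 |

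The simulation agrees with the formula in size and pattern.

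**The case against.** The strongest reply is that this is an exploratory analysis whose detail is deferred to the SAP. Section 2 calls the whole study primarily exploratory, and no power is claimed for biomarkers. Restricting later enrolment would need a defined subpopulation, so some grouping suits that purpose. Both sub-studies are non-randomised (Sections 12.6.3 and 13.6.3), so neither analysis can separate a predictive marker from a prognostic one. This stands, and it limits how much the point matters. It does not remove the point, because the protocol itself fixes grouping as the use of the selected markers and leaves only the details to the SAP.

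Three stronger readings are tempting, and the documents do not support them:

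- **That the cuts will be chosen after seeing the data.** Section 9.4 says each sub-study's SAP is finalised before any analysis is run. Missing cut-points in the protocol are therefore no evidence of post-hoc cuts.
- **That grouping is the only route from biomarkers to outcome.** Section 9.4.6 allows pooled modelling of exposure, biomarkers, safety and efficacy. It is optional and may be reported separately, so it is not a commitment, but it is a stated route. Nor does Section 9.4.4.1 forbid a measured-scale analysis.
- **That the plan costs about 20 points of power.** That size needs a median split and a measured-value analysis with roughly 65% to 90% power. The protocol states neither.

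A normal marker with a linear effect is also the most favourable case for the measured value. If the true relation were a threshold near the cut, this loss would not arise.

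**Conclusion.** The point holds in conditional form. Section 9.4.4.1 commits continuous biomarkers associated with response to subgroup analysis of the time-to-event endpoints, and it commits to no analysis on the measured scale. If such a marker is roughly normal with a linear log-hazard effect and is split at the median, about 36% of the information is lost. The cost in power then ranges from about 1 to 21 points over the cases examined, and it is largest where power would otherwise be moderate to high. The loss depends on the cut, as the table shows, and is nil for categorical markers.

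The normal distribution, linear effect, effect sizes and event counts are assumptions, not protocol figures. The primary analyses are untouched. This is a worthwhile but optional change.

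**What to change.** Amend Section 9.4.4.1, and carry the change into the SAP, along these lines:

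- Continuous baseline biomarkers carried forward to time-to-event analysis are analysed on their measured scale, log-transformed where skewed, in Cox models. The hazard ratio per SD and its 95% CI are reported as exploratory estimates, and linearity is checked.
- On-treatment values are analysed by landmark or as time-dependent covariates. PFS and OS are timed from first dose, so entering a later measurement as if it were known at the start would create immortal-time bias.
- Subgroup Kaplan-Meier curves are kept for display, at cut-points fixed in the SAP: TPS 1% and 50% for PD-L1, and pre-set values for other markers.

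The response screen stays as written, so the change does not open every measured marker to Cox testing.

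The cost is a few sentences and a little more analysis work. No extra data, visits or participants are needed. The downside is an assumed functional form, which the linearity check addresses.
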